## PROTOCOL SYNOPSIS

Protocol Number:	DS1040-A-J110
Investigational Product:	DS-1040b
Active Ingredient(s)/INN:	To be determined.
Study Title:	A phase 1, multicenter, randomized, single-blind, placebo-controlled, single-ascending dose study to assess the safety, pharmacokinetics, and pharmacodynamics of DS-1040b in acute ischemic stroke subjects with thrombectomy.
Study Phase:	Phase 1
Indication Under Investigation:	Acute ischemic stroke
Study Objectives:	
Primary objectives: To confirm the safety and tolerability of DS-1040b in patients with acute ischemic stroke in whom thrombectomy device treatment is indicated. The primary endpoints are the incidences of symptomatic and asymptomatic intracranial hemorrhage and non-intracranial (Thrombolysis in Myocardial Infarction [TIMI]) major bleeding.
 
Secondary objectives:
 

1. To measure plasma and urine drug concentrations and calculate pharmacokinetic parameters

2. To examine the effect of DS-1040b on fibrinolytic biomarkers (activated form of thrombin-activatable fibrinolysis inhibitor [TAFIa] activity, D-dimer level, and thrombin-activatable fibrinolysis inhibitor [TAFI] antigen level)

3. To assess the change in the National Institutes of Health Stroke Scale (NIHSS) score at 24 hours after the start of study drug administration relative to baseline and the proportion of subjects with good prognosis (modified Rankin Scale [mRS] score of 0 to 2) on Days 30 and 90

 
Type of study objectives: Safety/tolerability

Study Design:	
Type of study: Intervention
 
Type of intervention: Drug
 
Type of indication: Treatment
 
Study design: Parallel-cohort (a parallel-cohort ascending dose design)
 
Level of blindness: Single-blind
 
Type of comparator: Placebo
 
Treatment groups: Five groups (DS-1040b 0.6 mg, 1.2 mg, 2.4 mg, 4.8 mg, and placebo groups)
 
Randomization: Not applicable.
 
Stratification factors: Not applicable.
 
Allocation ratio: Only a DS-1040b group in the 0.6 mg cohort; and a ratio of DS-1040b: placebo = 3:1 per cohort for the 1.2 mg and higher dose cohorts
 
Duration of assessment of each subject: 90 days

	Addition to standard treatment: Applicable Standard treatment indicated: A stent-type thrombectomy device (stent retriever)
Study Duration:	01 Apr 2017 to 30 Jun 2020 Duration of study for each subject: 90 days Duration of study drug administration for each subject: 6 hours
Study Centers and Location:	20 centers in Japan
Subject Eligibility Criteria:	
Target disease: Acute ischemic stroke
 
Inclusion Criteria
 
Subjects must satisfy all of the following criteria at the time of informed consent to be included in the study:
 

1) Male or female aged 20 to < 90 years

2) Having acute ischemic stroke with intracranial artery (internal carotid artery [ICA] or middle cerebral artery [MCA] M1 region) occlusion confirmed by computed tomography angiography or magnetic resonance angiography

3) Thrombectomy can be performed in principle within 8 hours after the onset of ischemic stroke.

4) Receiving treatment with a stent-type thrombectomy device as the initial treatment

5) Having an NIHSS score of <math>\geq 6</math> and Alberta Stroke Program Early CT Score (ASPECTS) of <math>\geq 6</math>

 
Exclusion Criteria
 
Subjects who meet any of the following criteria will be disqualified from entering the study:
 

1) Having received or planned to receive treatment with a thrombolytic drug

2) Having intracranial or subarachnoid hemorrhage confirmed by head imaging (computed tomography [CT] or magnetic resonance imaging [MRI])

3) Having experienced a suspected bleeding event, such as gastrointestinal hemorrhage

4) Having a history of intracranial hemorrhage or a cerebral hemorrhage risk such as intracranial tumor, cerebral aneurysm, and cerebral arteriovenous malformation

5) Having a complication of aortic dissection

6) Having a history of serious head/spinal cord injury or surgery within 3 months

7) Having a history of gastrointestinal or urinary tract hemorrhage within 21 days

8) Having undergone major surgery or experienced serious non-head injury within 14 days

9) Having activated partial thromboplastin time (aPTT)

or partial thromboplastin time (PTT) of > 2 times the normal value

- 10) Having an international normalized ratio (INR) of > 1.7
- 11) Having a platelet count of < 100,000/mm^3
- 12) Having uncontrolled hypertension despite drug therapy (systolic > 185 mmHg and diastolic > 110 mmHg)
- 13) Having a baseline blood glucose level of > 400 mg/dL
- 14) Having occlusion of at least two major arteries
- 15) Treatment with a stent-type thrombectomy device is not indicated due to the presence of carotid artery dissection, occlusion/vasculitis of the entire carotid artery/neck, contrast media allergy, etc.
- 16) Having a severe hepatic disorder (fulminant hepatitis, hepatic cirrhosis, hepatic tumor, or other hepatic disorders meeting any of the following criteria)

Parameter	Criterion
Total bilirubin	>= 3.0 mg/dL
AST (GOT)	>= 2.5 × the upper limit of reference range or >= 100 U/L
ALT (GPT)	>= 2.5 × the upper limit of reference range or >= 100 U/L
ALP	>= 2.5 × the upper limit of reference range

- 17) Being on chronic dialysis or having a severe renal disorder (eg, nephrotic syndrome, acute/chronic renal failure, uremia, and hydronephrosis) or a serum creatinine level of >= 2 mg/dL
- 18) Having a history of ischemic stroke within 30 days prior to the study drug administration
- 19) Having received another study drug in another clinical study within 30 days prior to the study drug administration in this study
- 20) Being pregnant, having the potential of being pregnant, being breastfeeding, or planning to become pregnant (or having a partner who is planning to become pregnant) while participating in the study
- 21) Otherwise considered inappropriate for the study by the investigator or subinvestigator

Dosage Form, Dose and Route of Administration:

This study is an intergroup ascending dose study using a total of 4 cohorts. Four doses (0.6, 1.2, 2.4, and 4.8 mg) of DS-1040b will be used. The study drug will be administered intravenously over 6 hours. The 0.6 mg cohort will consist only of a DS-1040b group, to which 6 subjects (or 12 subjects) will be randomized. For other

---


dose cohorts, subjects will be randomized to the DS-1040b or placebo group in a 3:1 ratio. Details of the dosing regimen are provided below:
 
The required amount for injection will be removed from the vial and added to 100 mL of 0.9% saline. One-fourth (25%) of the entire amount will be administered intravenously over 30 minutes as a loading dose, followed by a 5.5-hour continuous intravenous infusion of the remaining injection (75%) as a maintenance dose. Administration of a loading dose will in principle be started before recanalization of the occluded vessel is achieved with a thrombectomy device; however, it may be started after the recanalization procedure if it is likely to be achieved prior to study drug administration.
	
Study Endpoints:	
Primary endpoints
 

✓ Incidence of symptomatic intracranial hemorrhage (defined by the European Cooperative Acute Stroke Study [ECASS])

✓ Incidence of asymptomatic intracranial hemorrhage

✓ Incidence of non-intracranial (TIMI) major bleeding

 
Secondary endpoints
 

✓ Blood and urine pharmacokinetics

✓ Fibrinolytic biomarkers (TAFIa activity, D-dimer level, and TAFI antigen level)

✓ Change in the NIHSS score at 24 hours after the start of study drug administration relative to baseline

✓ Proportion of subjects with good prognosis based on the mRS score (mRS score of 0 to 2) on Day 90

Planned Sample Size:	54 subjects (or 60 subjects) (6 or 12 subjects in the 0.6 mg cohort and 16 subjects per cohort in other dose cohorts [a total of 4 cohorts])
Statistical Analyses:	
The analytical objective of this study is to confirm the safety and tolerability of DS-1040b in patients with acute ischemic stroke. With regard to the safety, the point estimate and 95% confidence interval will be estimated for the incidences of symptomatic and asymptomatic intracranial hemorrhage events within 24 hours to 36 hours after the start of study drug administration and the incidence of non-intracranial (TIMI) major bleeding within 96 hours after the start of study drug administration. Data from the placebo groups in each cohort will be integrated and data from the DS-1040b groups will be summarized by dose.
 
Adaptive design: Not applicable.

---

---

Study Discontinuation Criteria	
If the following criterion is met, the study will not proceed to the next cohort and will be discontinued at that point:
 

✓ Occurrence of two events of symptomatic intracranial hemorrhage (as defined by ECASS)* not attributable to external factors at 36 hours after the start of DS-1040b administration in the DS-1040b group in one cohort

 
If any of the following criteria are met, the necessary actions to be taken to ensure the safety of subjects, including not proceeding to the next cohort, will be considered:
 

✓ Occurrence of one event of symptomatic intracranial hemorrhage (as defined by ECASS)* not attributable to external factors at 96 hours after the start of study drug administration in the DS-1040b group in one cohort

✓ Occurrence of one event of non-intracranial (TIMI) major bleeding* at 96 hours after the start of study drug administration in the DS-1040b group in one cohort

✓ Occurrence of any event requiring the consideration of study discontinuation, such as a severe organ disorder or treatment-related serious adverse event (SAE)

 
*The final assessment of symptomatic intracranial hemorrhage and (TIMI) major bleeding will be performed by the central adjudication committee member in a blinded fashion.
 
For events meeting any of the following criteria, the sponsor will discuss the matter with the medical expert as appropriate to decide whether or not the study should be discontinued:
 

• New information on the safety of the study drug or information on SAEs

• A major violation of Good Clinical Practice (GCP) or the clinical study protocol by either the sponsor, study center, or investigator

• Combined elevations of aminotransferase and bilirubin meeting the laboratory criteria for a potential case of Hy's Law

• Any other new information obtained during the study

--------------------------------	---

---

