### 4.2 Exclusion Criteria

Subjects who meet any of the following criteria will be disqualified from entering the

study:

- 1) Having received or planned to receive treatment with a thrombolytic drug (ie, urokinase or rt-PAs)
- 2) Having Intracranial or subarachnoid hemorrhage confirmed by head imaging (computed tomography [CT] or magnetic resonance imaging [MRI])
- 3) Having experienced a suspected bleeding event, such as gastrointestinal hemorrhage
- 4) Having a history of intracranial hemorrhage or a cerebral hemorrhage risk such as intracranial tumor, cerebral aneurysm, and cerebral arteriovenous malformation
- 5) Having a complication of aortic dissection
- 6) Having a history of serious head/spinal cord injury or surgery within 3 months
- 7) Having a history of gastrointestinal or urinary tract hemorrhage within 21 days
- 8) Having undergone a major surgery or experienced serious non-head injury within 14 days
- 9) Having activated partial thromboplastin time (aPTT) or partial thromboplastin time (PTT) of  $> 2$  times the normal value
- 10) Having an international normalized ratio (INR) of  $> 1.7$
- 11) Having a platelet count of  $< 100,000/\text{mm}^3$
- 12) Having uncontrolled hypertension despite drug therapy (systolic  $> 185 \text{ mmHg}$  and diastolic  $> 110 \text{ mmHg}$ )
- 13) Having a baseline blood glucose level of  $> 400 \text{ mg/dL}$
- 14) Having occlusion of at least two major arteries
- 15) Treatment with a stent-type thrombectomy device is not indicated due to the presence of carotid artery dissection, occlusion/vasculitis of the entire carotid artery/neck, contrast media allergy, etc.
- 16) Having a severe hepatic disorder (fulminant hepatitis, hepatic cirrhosis, hepatic tumor, or other hepatic disorders meeting any of the following criteria)

Parameter	Criterion
Total bilirubin	$\geq 3.0 \text{ mg/dL}$
AST (GOT)	$\geq 2.5 \times$ the upper limit of reference range or $\geq 100 \text{ U/L}$
ALT (GPT)	$\geq 2.5 \times$ the upper limit of reference range or $\geq 100 \text{ U/L}$
ALP	$\geq 2.5 \times$ the upper limit of reference range

- 17) Being on chronic dialysis or having a severe renal disorder (eg, nephrotic syndrome, acute/chronic renal failure, uremia, and hydronephrosis) or a serum creatinine level of  $\geq 2 \text{ mg/dL}$ .
- 18) Having a history of ischemic stroke within 30 days prior to the study drug

administration

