- 19) Having received another study drug in another clinical study within 30 days prior to the study drug administration in this study
- 20) Being pregnant, having the potential of being pregnant, being breastfeeding, or planning to become pregnant (or having a partner who is planning to become pregnant) while participating in the study
- 21) Otherwise considered inappropriate for the study by the investigator or subinvestigator

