**<Rationale>**

- 1) This criterion will be used because the safety of subjects cannot be ensured with absolute certainty due to insufficient data on the assessment of the bleeding risk associated with the combined use of DS-1040b and rt-PA therapy.
- 2) to 3) These criteria will be used because a potential worsening of existing bleeding events associated with the use of DS-1040b cannot be ruled out.
- 4) to 13) These criteria will be used to exclude patients at a high bleeding risk.
- 14) This criterion will be used in consideration of the potential effect of DS-1040b on the TICI grade as a reperfusion marker index.
- 15) This criterion will be used to appropriately enroll patients in whom stent placement is indicated.
- 16) to 18) These criteria will be used in consideration of the safety of subjects.
- 19) This criterion will be used in consideration of ethics and the safety of subjects.
- 20) This criterion will be used in consideration of ethics and the safety of subjects. Contraception with the use of the barrier method (spermicide condoms, intrauterine device, etc., approved or certified in Japan) will be required for at least 90 days after study drug administration.
- 21) This criterion will be used to allow the investigator or subinvestigator to determine the eligibility of subjects by taking other general factors into account.

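### Exclusion criterion 12 joins its blood-pressure limits with *and*, so read literally a treated patient above only one limit (eg, 220/90 or 180/120 mmHg) is not excluded

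*Combined protocol and SAP*

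**What the plan says.** Criterion 12 appears twice, with the same limits and the same conjunction. The synopsis has "Having uncontrolled hypertension despite drug therapy (systolic > 185 mmHg and diastolic > 110 mmHg"; Section 4.2 opens with the same words, "Having uncontrolled hypertension despite drug therapy", and repeats the bracketed limits.

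The rationale after Section 4.2 gives one purpose for criteria 4 to 13 together: "These criteria will be used to exclude patients at a high bleeding risk". It does not discuss blood pressure separately, and it does not say whether one limit or both must be exceeded.

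No other text sets a blood-pressure value for entry. Sections 6.1 and 6.11 and Table 18.1-1 provide for measuring and recording blood pressure, without a limit. The only other route to exclusion is criterion 21: "Otherwise considered inappropriate for the study by the investigator or subinvestigator".

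**The concern.** With *and*, neither limit does anything on its own. However high the systolic pressure, criterion 12 does not apply while the diastolic is at or below 110 mmHg. The same holds for any diastolic pressure while the systolic is at or below 185 mmHg. That fits poorly with a criterion listed among the bleeding-risk exclusions, in a trial whose primary endpoints (Section 7) are intracranial hemorrhage and major bleeding.

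Two things are at stake. The first is who is exposed: a center that follows the wording admits a patient above a limit that the sponsor itself set. The second is consistency. Twenty centers are planned, and Section 16.6 allows no waiver of a stated criterion except to remove an immediate hazard, so the wording is what centers are held to. If it can be read two ways, the same patient may count as eligible at one center and as a violation at another. Section 5.7.1 requires withdrawal of a subject found to violate an exclusion criterion, so the difference has a practical consequence.

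**Working it through.** The plan gives no figure to reproduce here; the check is of the rule's logic.

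**Inputs.** Systolic limit 185 mmHg and diastolic limit 110 mmHg, both strict (greater than), from criterion 12 in the synopsis and Section 4.2. The patient is assumed to be on drug therapy, as the criterion requires. The four test pressures are chosen for illustration.

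**Rule as written:** excluded if S > 185 and D > 110. **Rule with the other conjunction:** excluded if S > 185 or D > 110.

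| S/D (mmHg) | S > 185 | D > 110 | With *and* | With *or* |
|---|---|---|---|---|
| 186/111 | true | true | excluded | excluded |
| 220/90 | true | false | not excluded | excluded |
| 180/120 | false | true | not excluded | excluded |
| 185/110 | false | false | not excluded | not excluded |

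The wording as it stands excludes 1 of the 4; with *or*, 3 of the 4 are excluded. The two rules differ exactly for patients above one limit and not the other. These counts show where the rules part. They say nothing about how often such patients present.

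**Does another rule close the gap?** The lead-in to the exclusion list makes any one criterion sufficient, but that works between criteria and not inside criterion 12. Criterion 21 can remove the patient, but at the investigator's discretion and without a pressure value.

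**Does the drafting elsewhere settle the meaning?** Set side by side, the comparable places do not decide it:

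- Inclusion criterion 5 requires a minimum NIHSS "and Alberta Stroke Program Early CT Score (ASPECTS) of" at least 6. Here *and* means both, but this is an inclusion list in which everything must be satisfied anyway.
- Criterion 9 uses *or*: "Having activated partial thromboplastin time (aPTT) or partial thromboplastin time (PTT) of" more than twice normal. That is one threshold applied to alternative assays, not two measurements each with its own limit.
- Criterion 16 uses *or* for AST and ALT: 2.5 times "the upper limit of reference range or >= 100 U/L". Those are two cut-offs on one analyte.
- Criterion 4 lists "intracranial tumor, cerebral aneurysm, and cerebral arteriovenous malformation" as examples of hemorrhage risk, where any one suffices despite the *and*. Criterion 17 lists renal disorders in the same way.
- Section 12.4.2 explains severe renal impairment with a bracketed list of limits (BUN, creatinine, urine protein, potassium and others) that cannot sensibly require all of them at once.

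The first three lean toward reading the conjunctions literally, but none is a close match. The last two support a loose reading of a bracketed list. The literal reading is reasonable, but it is not the only one.

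**The case against.** The strongest reply is that the operative phrase is uncontrolled hypertension despite treatment, and that the bracket merely names the limit for each pressure. Read as criteria 4 and 17 and the list in Section 12.4.2 are read, criterion 12 excludes a patient above either limit and the gap disappears. This stands as a possible reading. It means that the documents establish an ambiguity, not a proven hole. It does not remove the need to act: if *or* was meant, the edit states the intent; if *and* was meant, the criterion lets 220/90 mmHg through.

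A second reply is that the harm is assumed. That also stands. Nowhere do the documents say that exceeding one limit alone marks a high bleeding risk.

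A third is that other safeguards exist. Sections 3.1 and 12.4.1 require one-by-one evaluation until three subjects aged 81 or older are in the DS-1040b group. Under Section 12.4.2 one symptomatic intracranial hemorrhage not attributable to external factors pauses enrollment for review, and two in the DS-1040b group of one cohort stop the study. These limit the consequences, but they act after exposure or after a bleed and do not screen blood pressure at entry.

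A reader might go further and infer that a rule is also needed on which reading counts, because Table 18.1-1 accepts vital signs taken before consent. That is a separate matter. The criterion's reference to hypertension persisting despite drug therapy already points to a reading under treatment, so no such requirement or repeat measurement is proposed here.

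**Conclusion.** The point holds as a defect of wording in a safety criterion. Read literally, criterion 12 does not exclude a treated patient above only one limit, and only the discretionary criterion 21 could then keep that patient out. Since a looser reading is open, the rule is at best ambiguous across the 20 centers. On the literal reading it only partly serves the stated bleeding-risk purpose: it still excludes patients above both limits.

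The conclusion rests on one assumption, that a pressure above a single limit signals high bleeding risk. This is inferred from the sponsor having set a limit for each pressure.

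No magnitude is claimed. The number of candidates above one limit only, and their bleeding risk, are not in the documents. A reader might infer that the wording will raise the observed bleeding rates or undermine the sample size or the two-event stopping rule. The documents give nothing from which to derive such an effect, and none is asserted. Nor do they show that the sponsor deliberately chose to admit such patients. The correction is worth making because it is nearly free and makes entry consistent whichever reading was intended.

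**What to change.** In criterion 12, in both the synopsis and Section 4.2, change the bracketed limits to: systolic > 185 mmHg *or* diastolic > 110 mmHg. Leave the reference to drug therapy as it is.

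The cost is one word in two places and possibly a few fewer eligible candidates; the documents do not allow that number to be estimated. No analysis, endpoint definition or stopping criterion needs to change.

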## LIST OF ABBREVIATIONS

ABBREVIATION	DEFINITION
ALP	alkaline phosphatase
ALT (GPT)	-alanine aminotransferase (glutamic pyruvic acid transaminase)
AHA	American Heart Association
aPTT	activated partial thromboplastin time
ASA	American Stroke Association
ASPECTS	Alberta Stroke Program Early CT Score
AST (GOT)	-aspartate aminotransferase (glutamic oxaloacetic acid transaminase)
AUC	area under the plasma concentration-time curve
AUC inf	area under the plasma concentration-time curve up to infinity
AUC last	area under the plasma concentration-time curve up to the last quantifiable time
BUN	blood urea nitrogen
C 0	initial plasma concentration
CK (CPK)	creatine kinase (creatine phosphokinase)
CL	total body clearance
CLcr	creatinine clearance
CLr	renal clearance
C max	maximum plasma concentration
CRO	contract research organization
CRP	C-reactive protein
CT	computed tomography
CYP	cytochrome P450
DAPT	dual antiplatelet therapy
DS-1040a	the free form of DS-1040b
EC	ethics committee
EC 50	50% effective concentration
ECASS	European Cooperative Acute Stroke Study
EC max	maximum effective concentration
EDC	electronic data capture
FAS	full analysis set
GCP	Good Clinical Practice
γ-GT	gamma-glutamyltransferase-
IC 90	90% inhibitory concentration
ICA	internal carotid artery
ICF	informed consent form
ICH	international conference on harmonization
INR	international normalized ratio
IRB	institutional review board
IRT	interactive response technology
LDH	lactic acid (lactate) dehydrogenase
MCA	middle cerebral artery
MedDRA	Medical Dictionary for Regulatory Activities
MRI	magnetic resonance imaging
mRS	modified Rankin Scale
NIHSS	National Institute of Health Stroke Scale
PT	prothrombin time
PTT	partial thromboplastin time
rt-PA	recombinant tissue plasminogen activator

ABBREVIATION	DEFINITION
SHR	spontaneously hypertensive rat
TAFI	thrombin-activatable fibrinolysis inhibitor
TAFIa	activated form of thrombin-activatable fibrinolysis inhibitor
TEAE	Treatment-emergent Adverse Event
TICI	Thrombolysis in Cerebral Infarction
TIMI	Thrombolysis in Myocardial Infarction
Vss	volume of distribution at steady state

